#### **8.3.5.1 LANDMARK PROGRESSION FREE SURVIVAL RATE**

Landmark Progression Free survival will be estimated at 6 months and 12 months, where applicable. Landmark analysis is one of most commonly used approaches for the analysis of these kinds of time-dependent covariates in time-to-event data. It considers responses up to and including a fixed landmark timepoint. The PFS rate at 6 and 12 months is the

number of subjects who did not progress and were alive at the 6 or 12 month timepoint over the number of subjects considered as evaluable and is displayed as a percentage.

#### 8.3.5.2 CENSORSHIP

In general, subjects are censored at the date of the last objective disease assessment that verified lack of disease progression if they are last known to be alive, on-treatment or within 28 days following treatment discontinuation, and progression-free. Censoring is explicitly described below:

- Subjects with inadequate/incomplete baseline disease assessment will be censored at the first dose date.
- Subjects not reassessed after first dose date will be censored at the date of first dose date unless death occurred prior to the first planned assessment (in which case the death is an event).
- Subjects with at least one on-study disease assessment who discontinue treatment without documented disease progression or death are censored at the date of the last objective disease assessment documenting no progression.

There are two exceptions:

- If objective progression or death is documented  $\leq$  28 days after discontinuation then progression or death is an event
- If a new anti-cancer treatment is started prior to objective progression and  $\leq$  28 days after discontinuation, then censorship is at the date of the last objective disease assessment that verified lack of disease progression prior to the new treatment

Subjects with documentation of progression or death after an unacceptably long interval (i.e., 2 or more missed or indeterminate/not evaluable assessments) since the last tumor assessment will be censored at the time of last objective assessment documenting no progression.

Table 4 Evaluation of Radiographic Disease Progression and Censoring

Situation	Date of	Outcome
Inadequate baseline tumor assessment		
No post-baseline assessment and no death prior to first scheduled assessment	First Dose Date	
Death or documented PD after $\geq$ 2 consecutively missed and/or not evaluable scheduled tumor assessments	Last tumor assessment documenting no PD	Censored
Alive, on-treatment, and no documented PD	Last tumor assessment documenting no PD	
Documented PD (on, prior to, or $\leq$ 28 days after treatment discontinuation)	First tumor assessment documenting PD	Progression (Event)

New anticancer treatment prior to PD	Last tumor assessment documenting no PD prior to new anticancer treatment	Censored
Treatment discontinuation due to toxicity, undocumented progression, or other reason	Last tumor assessment documenting no PD prior to discontinuation	Censored
Death prior to first scheduled assessment	Death	Death (Event)
Death without documented PD and $\leq$ 28 days after treatment discontinuation	Death	Death (Event)

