### **8.3.5 PROGRESSION-FREE SURVIVAL – INVESTIGATOR ASSESSED AND CENTRAL REVIEW**

The investigator will make tumor assessments and a separate independent central review will also be performed. All PFS calculations (months) will be the following:

$$[\text{Progression/Death/Censor Date} - \text{First Dose Date} + 1] / 30.4375.$$

PFS is defined as the number of months from the date of first dose to the date of death or documented (objective) disease progression via RECISTv1.1, whichever occurs earliest. Subjects that do not experience progression or death at the time of analysis will have time to progression censored at the date of last valid tumor assessment, which is defined as an overall response other than "not evaluable". The actual tumor assessment date (i.e., scan) will be used, not the reading date of the scan/assessment. If the tumor assessment is performed over multiple days for a documented disease progression, the first date will define the assessment date. If the subject is censored, the last date will define the assessment date. Again the "assessment date" will be defined as the "scan date" and not the overall response date. Tumor assessments are performed within 10 days prior to every 3rd cycle starting from cycle 4 (e.g., C4, C7, C10, etc.) until treatment discontinuation. Subjects discontinuing treatment due to reasons other than documented disease progression will have their tumor assessed (using the same modality that was used during study treatment) every 12 weeks ( $\pm$  2 weeks) for up to 2 years after the last treatment visit, until a) they start a new therapy for their cancer, b) death, c) withdrawal of consent, d) are lost to follow-up, e) the Sponsor notifies sites that tumor assessment is no longer required during long-term follow-up, or f) termination of study by the Sponsor.

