### **8.3.6 DURATION OF RESPONSE – INVESTIGATOR ASSESSED AND CENTRAL REVIEW**

Duration of response (DOR) is defined as the interval of time between date of first documented response (CR or PR with caveat of confirmation) to the earliest date of disease progression or death due to any cause, whichever occurs first. Censorship will be determined using the definitions in Section 8.3.5.2. DOR will be calculated for the subgroup of responder subjects.

$$[\text{Progression/Death/Censor Date} - \text{Date of First Response} + 1] / 30.4375.$$

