## **9. STATISTICAL ANALYSIS AND METHODOLOGY**

### **9.1 DISPOSITION OF SUBJECTS**

Frequency of patients enrolled, allocation to analysis populations and distribution by site will be tabulated. Frequencies and percentages of subject's treatment and study participation and final disposition will be reported overall and by site. Deaths while on-treatment (28 days post last dose, or start date of new anti-cancer drug therapy - 1, whichever is earlier) and off-treatment will be counted. Reason for end of treatment and end of study reasons will be summarized. Protocol deviations will be listed and major protocol deviations will be summarized.

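### Landmark PFS and OS are defined as crude proportions that conflict with the planned Kaplan-Meier analysis, and the PFS/DOR censor date after stopping treatment is not stated consistently

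*SAP*

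**What the plan says.** **Landmark rates.** SAP 8.3.5.1 and 8.3.7.1 each give a formula: subjects alive (and, for PFS, not progressed) at 6 or 12 months, divided by the subjects regarded as evaluable, shown as a percentage. SAP 9.11.3 says landmark PFS and landmark OS are described with Kaplan-Meier estimates and that PFS and OS use the SAF. SAP 7.12.1 asks for methods that allow for censoring.

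**PFS censoring.** SAP 8.3.5 gives the general definition: "PFS is defined as the number of months from the date of first dose to the date of death or documented (objective) disease progression". It adds: "Subjects that do not experience progression or death at the time of analysis will have time to progression censored". Subsection 8.3.5.2 then sets out censoring in detail, in three places that matter here:
- Its lead sentence describes subjects last known to be alive and progression-free while on treatment or within 28 days of stopping.
- Its bullet says subjects with an on-study assessment "who discontinue treatment without documented disease progression or death are censored at the date of the last objective disease assessment documenting no progression". The exception is that if progression or death is documented within "28 days after discontinuation then progression or death is an event".
- Table 4, for stopping because of toxicity, undocumented progression or another reason, gives the censor date as "Last tumor assessment documenting no PD prior to discontinuation".

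**DOR.** SAP 8.3.6 says: "Censorship will be determined using the definitions in Section 8.3.5.2".

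**Discontinuation date.** SAP 8.3.5.2 does not say which recorded date this is. Protocol 6.8 requires the date of stopping treatment in the eCRF. SAP 9.1 counts its own 28-day on-treatment window for deaths from last dose.

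**The concern.** A crude proportion is a valid landmark rate only if every subject is followed to the landmark or has the event first. Early censoring is to be expected here. Protocol 7.5 lets follow-up end through withdrawal, loss to follow-up, sponsor notice or study termination, and 8.3.5.2 itself censors most subjects who stop without progression. The formula does not say whether such subjects are successes, failures or excluded. Its denominator is also open: SAP 6.1.1 defines a Response Evaluable Set, but 9.11.3 assigns PFS and OS to the SAF.

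For the censor date, off-treatment scans continue every 12 weeks for up to 2 years, so the bullet and Table 4 diverge on data that are collected. If the bullet has no limit, it credits event-free time from scans on which progression would not count. Table 4 has the opposite mismatch: progression within 28 days of stopping is an event, but a clean scan in the same 28 days earns no time.

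SAP 3.1.4 lists PFS, DOR and both landmark rates under the Phase 2 primary efficacy objective. Two programmers following different passages could report different values from the same data.

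**Working it through.** The documents give no planned figure for these endpoints, so there is none to reproduce. The cohorts and subjects below are constructed to show what each rule does.

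**1. Twelve-month OS, 15 subjects (assumed).** Deaths at months 2, 3, 5, 7 and 9; censored at months 4, 6, 8 and 10; six alive at 12.
- Kaplan-Meier: (13/15)(11/12)(9/10)(7/8) = 0.626, or 63%.
- Proportion, censored counted as failures: 6/15 = 40%.
- Proportion, censored excluded: 6/11 = 55%.
- Proportion, censored counted as alive: 10/15 = 67%.

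**2. Six-month PFS, 15 subjects (assumed).** Six progress on day 63, two on day 126, four have no data after a clean day-63 scan, three are progression-free past 12 months.
- Kaplan-Meier: (9/15)(3/5) = 36%.
- Proportions: 3/15 = 20%, 3/11 = 27%, 7/15 = 47%.

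**3. Can progression on an off-treatment scan count?** Protocol 7.5 puts the first such scan at 84 ± 14 days, that is days 70 to 98 after last JTX-2011 dose. The Part C and D cohorts in SAP 3.1.4 are all q3w. For them the 28-day window closes on:
- day 0 + 28 = 28 if discontinuation is dated at last dose;
- day 21 + 28 = 49 if dated at the next planned dose;
- day 35 + 28 = 63 if dated at the latest End of Treatment visit.

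All fall before day 70. Progression first seen on an off-treatment scan could count only if discontinuation were dated 42 or more days after last dose (70 − 28). A scan at the End of Treatment visit (Protocol 7.4) can still count.

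**4. One q3w subject, PFS (assumed).** Last dose C6D1 = day 1 + 5 × 21 = 106, stops for toxicity. Clean scans on day 63, day 134 (End of Treatment, 106 + 28; required because the last scan was 71 days earlier) and day 190 (106 + 84). Progression on day 274 (106 + 168). No new therapy. Months = study day/30.4375.

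| Reading | Result |
|---|---|
| Bullet, no limit | censored day 190, 6.2 months |
| Bullet limited by the lead sentence, discontinuation = last dose | censored day 134, 4.4 months |
| Table 4, discontinuation = last or next planned dose | censored day 63, 2.1 months |
| 8.3.5 general definition alone | event day 274, 9.0 months |

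Put four such subjects in place of the four early-censored subjects in step 2. Six-month Kaplan-Meier PFS is then 36% under Table 4, and (9/15)(7/9) = 47% under either reading of the bullet. Four of 15 is a deliberately heavy case; one subject in 15 is 6.7 points.

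**5. DOR (assumed).** Response on day 63 confirmed on day 126, stops on day 130, clean scan on day 214, progression on day 298.
- Bullet, no limit: (214 − 63 + 1)/30.4375 = 5.0 months, censored.
- Table 4: (126 − 63 + 1)/30.4375 = 2.1 months, censored.
- Bullet limited to 28 days after stopping: also day 126, so the two agree for this subject.

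**The case against.** A reader might infer that PFS has three competing rules: 8.3.5, the bullet and Table 4. The documents do not support that. Section 8.3.5.2 is a subsection of 8.3.5 and announces that it sets censoring out explicitly, so the specific text governs the general. The bullets and Table 4 agree on the 28-day event window, and 8.3.6 sends DOR censoring to 8.3.5.2. A 28-day on-treatment rule is a recognised convention, not an error.

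Three further objections have force:
- The lead sentence of 8.3.5.2 supports reading the bullet as limited to 28 days after stopping, which narrows the gap with Table 4. The bullet itself states no limit, and Table 4 still differs for clean scans between stopping and day 28.
- A stopping date is collected, so the anchor is not absent. What is missing is a statement of which recorded date 8.3.5.2 uses.
- Kaplan-Meier for the landmarks is already planned in 9.11.3. This makes the fix easy but does not remove the explicit contrary formulas in 8.3.5.1 and 8.3.7.1.

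It is also true that there is no hypothesis testing (SAP 3.3.1), and that the expansion rule in SAP 9.12 rests on ORR.

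**Conclusion.** The point holds in two parts. The landmark formulas are wrong as written: under early censoring they can give a wrong rate, and they contradict 9.11.3. The illustrative spread is 40% to 67% against 63% for OS, and 20% to 47% against 36% for PFS. The censor date after stopping without progression is inconsistent between the bullet and Table 4, and DOR inherits this.

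A reader might also infer a known bias in reported PFS. The documents give no progression or discontinuation rates, and the answer changes with the rates assumed. Across 216 simulated scenarios (on-treatment median PFS 3 or 6 months, 15% to 35% stopping without progression, some starting new therapy), 12-month PFS under Table 4 is a median 0.7 points above the all-events result. In three other scenarios (median PFS/median time to stopping without progression of 3/12, 4/8 and 6/6 months, no new therapy) it is lower: 7.0% against 8.9%, 11.5% against 16.0%, and 22.6% against 30.0%. Neither size nor direction is established. ORR and the OS event definition are unaffected. The matter should be fixed because these are primary-objective summaries that must be reproducible.

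**What to change.** - **Landmarks.** In SAP 8.3.5.1 and 8.3.7.1, replace the proportions with the Kaplan-Meier estimates at 6 and 12 months on the SAF.
- **Censor date.** In both the 8.3.5.2 bullet and Table 4, use the last no-progression assessment on or before discontinuation plus 28 days, so that time at risk and countable events cover the same window. The PFS subject in step 4 is then censored on day 134 (4.4 months) under both, if discontinuation is last dose.
- **Anchor.** State which recorded date is discontinuation, for example last dose, as in SAP 9.1, or the stopping date collected under Protocol 6.8.
- **Precedence.** State in 8.3.5 that the 28-day rule in 8.3.5.2 governs the main PFS and DOR analysis.
- **Optional sensitivity analysis.** Count all RECIST progressions and deaths, still censoring at new anticancer therapy and after two or more consecutive missed or not-evaluable assessments. This is a useful addition, not the correction of an error.

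The cost is SAP wording and derivation code, since off-treatment scans and survival are already collected. In the sensitivity version some events are dated from 12-weekly rather than 9-weekly scans, and censoring at new therapy can still be informative.

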### **8.3.6 DURATION OF RESPONSE – INVESTIGATOR ASSESSED AND CENTRAL REVIEW**

Duration of response (DOR) is defined as the interval of time between date of first documented response (CR or PR with caveat of confirmation) to the earliest date of disease progression or death due to any cause, whichever occurs first. Censorship will be determined using the definitions in Section 8.3.5.2. DOR will be calculated for the subgroup of responder subjects.

$$[\text{Progression/Death/Censor Date} - \text{Date of First Response} + 1] / 30.4375.$$

### **8.3.7 OVERALL SURVIVAL**

Overall survival (OS) is defined as the interval of time from first dose date to the date of death for any cause. In the absence of confirmation of death, survival time will be censored at the last date the subject is known to be alive. OS calculations (months) will be the following:

$$[\text{Death/Censor Date} - \text{First Dose Date} + 1] / 30.4375.$$

#### **8.3.7.1 LANDMARK OVERALL SURVIVAL RATE**

Landmark Overall Survival will be estimated at 6 months and 12 months, where applicable. The OS rate at 6 and 12 months is defined as the number of subjects who were alive at the 6 or 12 month timepoint over the number of subjects considered as evaluable and is displayed as a percentage.

### **8.3.8 IMMUNE-RELATED RESPONSE CRITERIA**

Immune-related Response Criteria (irRC) as outlined below is based on/defined in the Guidelines for the Evaluation of Immune Therapy Activity in Solid Tumors: Immune-Related Response Criteria (Wolchok et al., 2009).

Table 5 Definitions of Response per irRC

Immune-Related Response	Definition by Timepoint
Complete Response (irCR)	Complete disappearance of all lesions (whether measurable or not, and no new lesions) Need confirmation by a repeat, consecutive assessment at least 4 weeks from the date first documented
Partial Response (irPR)	At least a 50% decrease in decrease in tumor burden (sum of the product of perpendicular diameters (SPD) of measurable lesions) relative to baseline  Need confirmation by a consecutive assessment at least 4 weeks after first documentation
Stable Disease (irSD)	Not meeting criteria for irCR or irPR, in absence of irPD
Progressive Disease (irPD)	At least a 25% increase in tumor burden (SPD of measurable lesions) relative to nadir (minimum recorded tumor burden)  Need confirmation by a repeat, consecutive assessment no less than 4 weeks from the date first documented

### 8.3.9 IMMUNE-RELATED OBJECTIVE RESPONSE RATE – CENTRAL REVIEW

Immune-related best overall response (irBOR) will only be evaluated according to central review. The irBOR (as defined by irRC guidelines) is recorded from first dose date until documented disease progression (irPD) or death. The irORR is defined as the proportion of subjects with an irBOR characterized as either a confirmed complete response (irCR) or confirmed partial response (irPR) prior to the initiation of subsequent anticancer treatment or prior to discontinuation of treatment (due to any other reason), whichever is earlier; irORR will be calculated relative to the total number of evaluable subjects. Subjects without baseline tumor assessments will be considered non-evaluable for this analysis.

## 8.4 PHARMACODYNAMIC ENDPOINT

### 8.4.1 ICOS TARGET ENGAGEMENT

ICOS target engagement on CD4 T cells is considered as a primary pharmacodynamic endpoint for both Phase 1 and Phase 2.

ICOS target engagement is measured by a receptor occupancy assay in peripheral blood mononuclear cells collected pre-treatment and at multiple time points on study. The baseline pre-treatment sample is considered to have 100% ICOS available, and all subsequent timepoints are reported as a % of the baseline ICOS score. Target engagement will be used to select the dose for safety/PK/Pharmacodynamics expansion cohorts AP1, AP2, BP1, BP2, and the RP2D.

#### **8.4.2 PREDICTIVE BIOMARKER ENDPOINTS**

##### **8.4.2.1 ICOS EXPRESSION BY IHC**

Tumor biopsy samples may be available for each subject in two ways; as an archived sample and or as a fresh (in study pre-treatment) sample. Biopsies will be analysed by Neogenomics using a validated assay to estimate the percentage of ICOS expressing immune cells in the sample. Where the percentage of cells is less than 1%, the ICOS IHC score will be set to 0. Where the percentage is greater than or equal to 1% and less than 5%, the ICOS IHC score will be set to 1. Where the percentage is greater than or equal to 5% and less than 15%, the ICOS IHC score will be set to 2 and where the percentage is 15% or greater, the ICOS IHC score will be set to 3. Missing ICOS values will not be classified.

ICOS high/low subgroups will be determined using the Neogenomics data as described above, with ICOS high subgroups represented by ICOS IHC score of 2 or 3 and ICOS low subgroups represented by ICOS IHC score of 0 or 1. ICOS subgroups may also be formed by grouping ICOS IHC score of 1, 2, and 3 together and using ICOS 0 as a separate subgroup. Missing ICOS values will not be imputed and any analysis using these will have the category ICOS high/low missing. Please refer to section 9.11.5 for subgroup analysis.

## **9. STATISTICAL ANALYSIS AND METHODOLOGY**

### **9.1 DISPOSITION OF SUBJECTS**

Frequency of patients enrolled, allocation to analysis populations and distribution by site will be tabulated. Frequencies and percentages of subject's treatment and study participation and final disposition will be reported overall and by site. Deaths while on-treatment (28 days post last dose, or start date of new anti-cancer drug therapy - 1, whichever is earlier) and off-treatment will be counted. Reason for end of treatment and end of study reasons will be summarized. Protocol deviations will be listed and major protocol deviations will be summarized.

### **9.2 DEMOGRAPHIC AND BASELINE CHARACTERISTICS**

The following demographic and baseline characteristics will be summarized:

- Continuous variables: Age [years], weight [kg], height, body mass index [kg/m^2], duration of disease since first diagnosis (at time of screening) [months], time since last anti-cancer treatment prior to study enrollment [months].
- Categorical variables: Age group [ $\leq 50$ , 50 to  $\leq 65$ ,  $> 65$ ], gender, race, ethnicity, ECOG performance status [0/1/2/3/4/5], smoking status [Never/Current/Former], prior IO therapy [Yes/No], prior IO refractory status [Yes/No], Prior PD-1 or PD-L1 therapy [Yes/No], ICOS IHC score in archived sample and fresh sample [0/1/2/3/NE], histological subtype, Total Proportion Score (TPS)  $\geq 1\%$  [Yes/No], TPS  $\geq 50\%$  [Yes/No], Combined Positive Score (CPS)  $\geq 1\%$  [Yes/No] and CPS  $\geq 10\%$  [Yes/No] for archival tumor samples.

### **9.3 MEDICAL HISTORY**

Medical history summaries will include tumor type at primary diagnosis and medical history by SOC and PT. Prior surgeries by type and location will be summarized. Baseline tumor assessment and disease sites will also be summarized. Data will be provided in subject listings.

### **9.4 PRIOR THERAPY**

Prior systemic lines of therapy and prior immunotherapies will be summarized using data as collected in the eCRF. The following will be summarized categorically for each unless stated as a continuous parameter.

- Number and type of prior systemic therapies and prior best response
- Number and type of prior immunotherapies

Medical review will be used determine the assignment of prior anti-cancer treatment categories and regimen. The final list of this determination will be maintained in the trial master file and signed by the study Medical Director.

Data as collected in eCRF will be provided in subject listings.

### **9.5 RADIOTHERAPY**

Prior radiotherapy will be summarized using data as collected in the eCRF. The following will be summarized categorically unless stated as a continuous parameter.

- Location of radiotherapy by body site
- Average total dose (by unit) as recorded by body site

## **9.6 CONCOMITANT MEDICATION**

Concomitant Medications will be summarized by ATC and PT using WHO Drug Version SEP2016. Prior and concomitant medications will be listed.

## **9.7 DURATION OF TREATMENT AND IN-STUDY PARTICIPATION**

Subject participation will be summarized using descriptive statistics. Intervals are defined as follows; first dose of study drug to end of study treatment, first dose of study drug to end of study participation and first dose of study drug to death, when reported.

